
(b) Hypotheses

Primary Hypothesis: Real-time maximum insertion pain (RTMIP) is significantly lower in both male and female Veterans examined by WECAC compared with WE.

Secondary Hypotheses: WECAC will show a significantly higher proportion with no pain, shorter insertion time and higher proximal colon ADR than WE alone in both male and female Veterans.

Exploratory hypotheses: Co-variables affect Veterans' report of RTMIP.

(c) Specific Objectives

a. To determine if WECAC significantly reduces RTMIP in both genders, to identify baseline patientand procedure characteristics that predict low RTMIP, and to assess impact on secondary outcomes. b. If WECAC increases *proximal colon* ADR, we will prepare for a multi-site VA cooperative study. The goal is to assess the hypothesis that WECAC, by increasing *proximal colon ADR*, can reduce the occurrence of post colonoscopy colon cancer (interval cancer) particularly *in the proximal colon*. This long term objective in the unsedated Veterans will be facilitated by identifying the least painful insertion method.

(2) Background and Significance (a) Background

Colonoscopy with air began without sedation. Insertion pain limited success in ~20% (13,23,24). Widespread use of sedation followed (13,23,24). In for-profit settings, anesthesiologist administered propofol is a major revenue stream; but has attracted criticisms (28). The VA focus on patient-centered care, teaching, efficacy, efficiency, and research data to support the mission, underpin efforts to discover technique(s) to attenuate RTMIP in unsedated Veterans. High quality (29) [higher proportion completing colonoscopy with no pain, shorter insertion time, proximal colon ADR] further strengthens appeal.

Factors linked to increased pain in unsedated cases reviewed by the PI (30) include: female, low body mass index (BMI) (≤25), female with low BMI, younger age (≤40 or ≤20 years), older age (>80 years), anxiety and anticipating discomfort; history of abdominal surgery, diverticulosis, diverticulitis, incomplete colonoscopy, and irritable bowel; difficult anatomy, inflammatory bowel symptoms, technically difficult insertion, lower gastrointestinal bleeding, obstructing malignancy, and following gastroscopy.

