D	WE	36/14/0	8	34%	26	40%	1.5 (0.7)		19 (11)
Fı	Frequency count; (%), % of total; mean (SD); L, liters; blank cell=data not listed in reports.								

Table 7 shows that indications were variable. WECAC required 1-2 L infusion; equivalent volume suctioned upon cecal arrival, confirming infused water suctioned mostly during insertion. Position change (25% vs. 34%) and abdominal pressure (37% vs. 40%) were needed less often with WECAC than in WE.

4. VA Palo Alto Healthcare System (Participant - [name] and others)

In 229 male Veterans successful minimal-sedation was 51% (water immersion) vs. 28% (air), P=0.0004, less pain (4.1±2.7 vs. 5.3±2.7; P=0.001) (56). Pl's coaching (42) led [name] to use WE (57). After coaching (42) co-investigator [name] has adopted WE (no formal published data).

(e) Significant correlation between RTMIP and recalled maximum insertion pain (PD/PI, [name])

The PI (5) and collaborators (3,4) have reproducibly confirmed that RTMIP (unblinded) is uniformly higher than recalled maximum insertion pain (blinded) and the 2 measures are significantly correlated (26).

(4) Work Proposed

(a) Study type descriptor. Prospective, multisite, multi-investigator, RCT, single (patient) blinded. Sites (no. investigators). VA: VAGLAHS (n=3); VAPAHCS (n=2); VANCHCS (n=2).

(b) Research design, methods and procedures to be used to accomplish the specific aims.

The investigators will describe the study at local lectures. The research coordinators will distribute flyers about the RCT to practitioners in primary care clinics, and will work closely with the colonoscopy schedulers to identify potential candidates (no escort, preference for no sedation). For scheduled unsedated Veterans, the coordinator will send each patient material (e.g. summary description, consent form) related to the RCT, with a follow up phone call to address questions that the Veterans may have. At all sites, Women's Health Clinics will assist the coordinators, to inform female Veterans of the scheduled unsedated option.

Inclusion criteria. *Informed/educated (about pros and cons of the unsedated option)* male and female *Veterans* (18-80 years old) undergoing diagnostic (positive stool occult blood test in the context of screening), surveillance (follow up of polyps) or screening (first-time) colonoscopy at participating sites, choosing scheduled unsedated colonoscopy for any reason (lack of escort, personal preference).

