Primary outcome. Patient with insertion pain that cannot be brought to a tolerable level by colonoscopist implemented maneuvers will be considered failure of cecal intubation and the insertion will be discontinued. The pain level at the time of discontinuation will be noted for analysis.

Standardized validated instruments.

Proportion with no insertion pain, insertion time, proximal colon ADR (secondary outcomes in males) have been defined above; demographic data, co-morbidities, prior history and additional procedure based and patient level parameters will be analyzed as covariables (Tables 9 and 10).

Table 9: Demographic variables, co-morbidities and prior history				
Age	In years		Hemorrhoids	0=no, 1=yes
Gender	Male, female		Chronic pain treatments	0=no, 1=yes

Education	Elementary, high, college, graduate	Substance abuse	0=no, 1=yes
Ethnicity	White, Black, Hispanic, Asian, other	Prior abdominal surgery	0=no, 1=Yes (type)
BMI	Weight/height ²	Prior sedation colonoscopy	0=no, 1=yes
Indication	Screening, surveillance, diagnostic, pain	Prior unsedated colonoscopy	0=no, 1=yes

Table 10: Additional procedure based and patient level covariates				
Recalled maximum insertion pain	Maximum pain during insertion reported to a blinded observer after			
score (blinded data)	colonoscopy before discharge, VAS: 0=none, 10=most severe. Correlation with RTMIP.			
Overall ADR - entire colon	Proportion of patients with at least one adenoma of any size.			
Right colon ADR	ADR from cecum to hepatic flexure			
Adequacy of patient blinding	Patient guesses which method is used (<60% correct=adequate).			
Successful cecal intubation	0=no, 1=yes			
Successful cecal ilitubation	Abdominal pain prior to start of colonoscopy: 0, none to 3, severe (recorded			
Current abdominal discomfort	before examination)			
Loop reduction maneuvers	Number of times used, recorded by nurse assistant			
Position change	Start with left lateral, change as needed to supine, right lateral, prone.			
Abdominal compression	0=no, 1=Yes (sigmoid, transverse, hepatic, right side)			
Need to change technique	0=no, 1=yes (to air insufflation)			
Water volumes (insertion) Volume of water (infused and suctioned) upon arrival to the cecum, eq				
	volumes confirm appropriate application of water exchange			
Water volumes (total)	Volume of water (infused and suctioned) at the end of colonoscopy			
	Documented during withdrawal (4=excellent, no residual stool; 3=good, small			

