Quality of bowel preparation	amount of residual stool; 2=fair, moderate amount of residual stool; 1=poor,			
	large amount of residual stool) (5)			
Failed (poor prep)	No. of patients in whom the cecum is not reached due to poor prep			
	Based on playback review of recorded procedure by blinded observer and			
Video data	tabulation of pertinent variables described above. Insertion and withdrawal			
	phase will be separately coded for blinded review			
Patient satisfaction	0=not satisfied, 10=very satisfied			
Willing to repeat same in future	0=not willing, 10=willing. Recorded by blinded observer prior to discharge.			
Recommend to family/friends	0=not willing, 10=willing. Recorded by blinded observer prior to discharge.			
Participant satisfaction	0=Not satisfied, 10=satisfied			
Reason for choice of unsedated	No ride, personal preference, other			
Abdominal discomfort today	0=none to 3=severe (recorded before examination)			
Expectation today	0=poor to 4=excellent (recorded before examination)			
Previous endoscopy experience	0=poor to 4=excellent (recorded before examination)			
Pain tolerance (patient reported)	0=poor to 4=excellent (recorded before examination)			
Subjective anxiety	0=none to 3=high (recorded before examination)			
Objective anxiety	0=none to 3=high (assessed by endoscopist before examination)			

Record keeping: A digital video recorder will be used to record the procedure to document procedure times (insertion, arrival in the cecal, biopsy, polypectomy, end of examination), cecal intubation (touching cecal floor) and the findings during the withdrawal phase. The digital images will bear no personal identifier.

Links. Enrolled patients will be randomized to 2 groups for examination. We can determine if WECAC will be superior to WE alone in providing low insertion pain. The influence of covariables on results of treatment can also be determined. The CONSORT guideline will be followed in reporting the data.

Standardization: During the start-up period, the PI will re-visit each site to facilitate standardization of WE and WECAC, and use of loop reduction, position change and abdominal compression maneuvers.

(f) Data collection methods, intervals, and follow-up procedures:

Prospective data gathering. Table 11 shows measures, their purposes, timing of data collection.

Table 11: Data to be monitored ^a	Baseline	During or after Colonoscopy	Up to 1 month follow up ^b

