Primary hypothesis. Real-time maximum insertion pain (RTMIP) is significantly lower in the patients examined by the WECAC technique compared with the WE technique. The analysis will compare 2 groups (WECAC vs. WE) with a two sample t-test. If the data show substantial non-normality (as in a prior dataset with WE (5)); we will compare the groups with a Mann-Whitney *U* test; P<0.0492 considered significant. Secondary analysis of the primary outcome will utilize mixed effects regression models to evaluate the effects of potential covariates/confounds described in Tables 9 and 10. First, we will assess the effect of each individual covariate in regression models including the effect for group assignment and gender (stratification factor in the randomization), as well as the covariate by group interaction. Next, we will construct a multiple regression model with the set of covariates found to be significant (either as a main effect or an interaction effect) in an overall regression model along with group assignment.

Dependent Variables	Variable Type	Analysis method
Primary Outcome		
RTMIP (0=none,	Continuous	2 sample Student t test. However, if distribution of the data is skewed as
10=most severe)	Continuous	seen in an earlier study (5), the Mann-Whitney U test will be used.

We have updated the analytic plan to include multi-level random effects (hierarchical model) for study site and provider within site. We will include two levels of random effects in this model: 1. random effects for study site, 2. random effects for provider which will be nested within sites.

Secondary hypotheses. WECAC produces significantly higher quality colonoscopy outcomes. For example, when WE alone and WECAC are compared, the proportion completing colonoscopy with no pain, insertion time, and ADR in the proximal colon will be significantly different. For continuous secondary outcomes (e.g. insertion time), we will use a similar analysis strategy as that used for the primary outcome. For dichotomous secondary outcomes (e.g., no pain, proximal colon ADR) we will use Chi-square tests to compare the outcomes between the groups. Generalized logistic models will be used to adjust for covariates, gender and study site for these outcomes.

Dependent Variables	Variable Type	Analysis method
Insertion time	Continuous	Student t test
No insertion pain (yes, no); proximal colon adenoma detection (yes, no)	Binary	Chi square

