Exploratory hypotheses. Co-variables affect patients' report of RTMIP. Patient-related factors include age, gender, ethnicity, education, BMI, indication for colonoscopy, current symptomatic hemorrhoids,

Dependent Variables	Variable	Analysis method		
Primary Outcome				
RTMIP	Continuous	Mixed effects regression, predict lower insertion pain, predictors-covariables		
Co-variables			Variable	Analysis method
Recalled maximum inse	Recalled maximum insertion pain score (blinded) [validates primary]			Correlate RTMIP
Body mass index (yes, no)			Continuous	
Age (<40 years) (yes, no); gender (male, female); ethnicity (White, Black, Hispanic, Asian, other) (yes, no); indication (Screening, surveillance, diagnostic); hemorrhoids (yes, no); chronic pain treatments (yes, no); substance abuse (yes, no); prior abdominal surgery (yes, no), sedation colonoscopy (yes, no), unsedated colonoscopy (yes, no), painful colonoscopy (yes, no); diverticulitis (yes, no); indication (abdominal pain) (yes, no); anticipation of pain (yes, no);  Exploratory variables			Binary	
Staff satisfaction (0=not satisfied to 10=very satisfied)			Continuous	
Adequacy of patient blinding (yes, no); Loop reduction maneuvers (yes, no); Position change (yes, no); Abdominal compression (yes, no); Need to change technique (yes, no); Failed (poor prep) (yes, no); Pain tolerance (patient reported) (0=low, 1=high); Reason for unsedated (no ride, personal preference, other) (yes, no); Previous endoscopy experience (0=not good, 1=good); Objective anxiety (0=none, 1=high) (by endoscopist before examination); overall adenoma detection - entire colon (yes, no);			Binary	

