chronic pain treatment, substance abuse, prior abdominal surgery, prior colonoscopy with or without sedation, current abdominal discomfort, expectation on day of colonoscopy, patient reported pain tolerance and subjective anxiety, objective anxiety assessed by colonoscopist, and reason for choice of no sedation. Procedure-related factors include technique of insertion, use of loop reduction maneuvers by the colonoscopist, change of patient position, application of abdominal compression by the assistant and insertion time, and length of colonoscope needed to reach the cecum. Examples: patients are more likely to report higher RTMIP amongst those with younger age, longer duration of insertion, lower expectation of painless insertion, female gender, low BMI, more frequent need for position change or abdominal compression. More patients will report lower RTMIP if there is low patient anxiety, good expectation of today's examination, no

prior abdominal surgery, colonoscopist use loop reduction maneuvers. The analysis of the exploratory outcomes will follow the same structure as the primary and secondary outcomes. To control for the multiplicity of exploratory outcomes we use the false-discovery rate (FDR) of Benjamini and Hochberg (67) rather than the traditional Bonferroni adjustment. The FDR assesses estimates the proportion of significant findings that are false positive results. The FDR method is less conservative and better preserves our ability to detect differences between groups.

Interim analysis. After 50% of subjects complete the protocol and data collection we will perform an inferential analysis of the primary endpoint as described in the statistical methods section. The only difference between the interim analysis of the primary endpoint and the final analysis will be the level of significance of the tests. If there is a significant treatment effect, this would communicated to the study Data and Safety Monitoring Board (DSMB) to consider early termination for efficacy.

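### The SAP's exploratory table types six predictors as yes/no although finer data are collected, in conflict with its own mixed-model text; the under-40 age term is practically untestable

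*SAP*

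**What the plan says.** The table under Exploratory hypotheses in the SAP gives a variable type for each predictor of real-time maximum insertion pain (RTMIP). Its binary block includes "Age (<40 years) (yes, no"), loop reduction, position change, pain tolerance (low or high), previous endoscopy experience (not good or good) and "Objective anxiety (0=none, 1=high) (by endoscopist before examination").

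The protocol collects finer data:

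- Table 9 records age in years.
- Table 10 records loop reduction as "Number of times used, recorded by nurse assistant".
- The Adjunct maneuvers paragraph says that counts will be kept for analysis for loop reduction, position change and abdominal compression.
- Table 10 scores pain tolerance and previous endoscopy experience from 0 to 4.
- Table 10 scores objective anxiety as "0=none to 3=high (assessed by endoscopist before examination").

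Under Primary hypothesis, the SAP says the mixed-effects models will "evaluate the effects of potential covariates/confounds described in Tables 9 and 10". Those tables hold the full-scale definitions. Each covariate is to be tested with its interaction with group, and the significant ones go into a multiple regression model.

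The SAP gives as an example that "patients are more likely to report higher RTMIP amongst those with younger age". Identifying characteristics that predict low RTMIP is part of the protocol's first specific objective.

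**The concern.** Two parts of the SAP describe the same predictors differently, and an analyst could follow either.

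The matter is most serious for age. A cut at 40 in a population with a mean age in the sixties leaves almost nobody in the younger group. The model also asks for an age-by-group interaction, so those few patients would be divided again between the arms. If all of them fell in one arm, the interaction could not be estimated.

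For the three ratings, the table does not say where the scale is cut. Objective anxiety has only none and high, which leaves scores 1 and 2 unassigned. Pain tolerance and previous experience have two labels for five levels. A cut chosen after the data are seen, in a procedure that keeps covariates by their significance, would weaken any predictor that it selects.

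What is at stake is the predictor part of the first objective. The treatment comparison is not touched.

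**Working it through.** **The plan's own figures.** The documents state neither the share of patients under 40 nor the power of the predictor models. The relevant stated figures are the sample sizes.

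- Men: a difference of 1.2/2.2 SD, two-sided alpha 0.0492 and 90% power give 71 per group by the normal formula and 72 by the exact t calculation. The SAP states 72, so 144 in total; 144/0.9 = 160 recruited.
- Women: 0.7 SD gives 44 by the normal formula (45 by t), and 2.7/3.7 SD gives 40 (41 by t). The SAP states 43, so 86 in total; 86/0.9 = 95.6, rounded up to 96.
- Recruited: 160 + 96 = 256. Evaluable: 144 + 86 = 230.

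**Share under 40.** Inputs are the mean (SD) ages in protocol Table 6. The share is Φ((40 − mean)/SD).

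| Cohort | n | Age, mean (SD) | z | Share under 40 | × 256 |
|---|---|---|---|---|---|
| A | 45 | 62 (10) | −2.20 | 1.39% | 3.6 |
| B | 26 | 64 (8) | −3.00 | 0.13% | 0.3 |
| C | 42 | 66 (9) | −2.89 | 0.19% | 0.5 |
| D | 50 | 61 (7) | −3.00 | 0.13% | 0.3 |

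Weighted by n (163 patients) the share is 0.50%, or 0.0050 × 256 ≈ 1.3 patients. The chance that none of 256 is under 40 is (1 − 0.00497)^256 ≈ 28%. Truncating at the eligibility limits of 18 and 80 moves cohort A only to 1.44%.

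**Younger women (assumption).** Cohorts A, C and D are described as male, and the documents give no ages for women. Keep the men at 0.50% (160 × 0.00497 = 0.8 patients) and give the 96 women an SD of 10:

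| Assumed mean age of women | Women under 40 | Share of all 256 |
|---|---|---|
| 62 | 1.3 | 0.8% |
| 58 | 3.4 | 1.7% |
| 55 | 6.4 | 2.8% |
| 50 | 15.2 | 6.3% (about 16 patients) |

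**Detectable difference with the cut.** At 80% power, two-sided 0.05, SD 2.2 and k of 230 patients under 40, it is (1.96 + 0.84) × 2.2 × √(1/k + 1/(230 − k)). On the 0-10 scale this gives 6.2 points for k = 1, 4.4 for k = 2, 3.6 for k = 3 and 3.1 for k = 4. The SD of 2.2 is the male pilot value. With an SD of 3 the ends of the range become 8.4 and 4.2.

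**Power with and without the cut.** Suppose age is normal and RTMIP is linear in age with correlation r. Cutting at a share p multiplies r by φ(c)/√(p(1 − p)), where c = Φ⁻¹(p). The factor is 0.205 at p = 0.5%, 0.268 at 1% and 0.303 at 1.4%. Squared, these keep 4%, 7% and 9% of the information. Power by Fisher's z is Φ(atanh(r)·√227 − 1.96):

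| Assumed r | Age in years | Cut, p = 0.5% | Cut, p = 1.4% |
|---|---|---|---|
| 0.15 | 62% | 7% | 10% |
| 0.20 | 86% | 9% | 15% |
| 0.25 | 97% | 12% | 21% |

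At p = 6.3% the factor is about 0.51, so r = 0.20 becomes about 0.10. Power is Φ(0.102 × 15.07 − 1.96) = Φ(−0.42) ≈ 34%. These figures are for a single predictor, before the false-discovery-rate adjustment and without the random effects.

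**The case against.** **The models already use the full scales.** The mixed-model text points to Tables 9 and 10, so one could say that the exploratory table only lists labels. The labels are indeed loose: body mass index is marked yes/no but typed continuous, and multi-category ethnicity and indication sit in the binary block. This stands to the extent that a settled plan to dichotomise is not established. It does not remove the conflict, because the exploratory table is the only place in the SAP that gives variable types for these predictors.

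**The cut has a source.** The protocol's Background cites "younger age (≤40 or ≤20 years), older age (>80 years") as pain factors. If the true effect were a step at 40, the cut would have the right form. The number of patients below it would still be the limit, as the detectable differences show.

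**The predictor hypotheses fail as a whole.** A reader might infer this, but the documents do not support it. Body mass index is typed continuous. Insertion time, expectation and subjective anxiety are not cut in the table. Gender and prior abdominal surgery are natively yes/no, and Table 10 collects abdominal compression as yes/no with site. The loop-reduction example concerns use, which a yes/no variable can address. It might also be suspected that nearly every patient would score yes on loop reduction, since Table 8 makes it part of both techniques, but the documents give no rate.

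**Age needs a curved term.** The Background names both ends of the age range. However, its older group is over 80, and eligibility is "18-80 years old) undergoing diagnostic" (or surveillance or screening) colonoscopy, so that group cannot be enrolled.

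**The loss for the other scales can be quantified.** The familiar 64% for a median split applies to a normal predictor. It does not carry over to short ordinal scores or counts with unstated cuts.

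**Conclusion.** The point holds as a minor one. The SAP gives conflicting codings for six predictors, and the yes/no version discards data that the trial collects.

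Only the younger-age hypothesis comes close to being untestable. With the pilot ages, about 0.3-3.6 of 256 patients would be under 40, and the cut would keep roughly 4-9% of the information in age. This rests on essentially male cohorts and a normal shape. The upper end comes from cohort A, which included a site in Taiwan and on-demand unsedated cases. If the women averaged 50 years, the share could reach about 6%; the test would then be possible but weak. A still lower mean or wider spread would raise the share further. The power comparison also assumes a linear age effect with r between 0.15 and 0.25.

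For the other five variables the loss is real but not quantified, and their tests remain usable. The primary comparison, its significance level and the sample size are unaffected.

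**What to change.** In the exploratory table of the SAP, replace the binary codings of these six variables so that the table agrees with the mixed-model text and with Tables 9 and 10:

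- Age: continuous, in years. A linear term is enough; no spline is required.
- Loop reduction and position change: number of times used, where recorded.
- Pain tolerance and previous endoscopy experience: ordinal scores, 0 to 4.
- Objective anxiety: ordinal score, 0 to 3.

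Add one sentence saying that covariates enter the mixed models on their collected scales. Leave natively yes/no variables as they are. For abdominal compression, keep the yes/no item in Table 10, or use the count promised under Adjunct maneuvers if it is recorded.

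The change costs only SAP wording. It needs no new data, patients or visits.

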Exclusion criteria. Decline to be randomized, unable to give consent or respond to questionnaires, history of colon surgery, active inflammatory bowel disease, lower gastrointestinal bleeding (except for occult blood or FIT positive in the context of colon cancer screening), therapeutic colonoscopy (e.g., hemostasis, removal of large polyp), proctosigmoidoscopy, bidirectional endoscopy, inadequate consumption of bowel preparation, known history of severe diverticulosis or diverticulitis, history of abdominal surgery previously requiring sedation for colonoscopy, current narcotic/anxiolytic medication use, prior unsuccessful experience with unsedated colonoscopy, emergent colonoscopy, evidence of colonic obstruction based on pre-colonoscopy clinical evaluation, current participation in other studies, medical condition that could increase the risk associated with colonoscopy (e.g., active cardiac or pulmonary disease or other serious disease), medical condition that would preclude a benefit from colonoscopic screening (e.g., cancer or any terminal illness), prosthetic heart valve, anticoagulant therapy, nonmedical problems (e.g., psychiatric disorders, excessive use of alcohol), need for special precautions in performing colonoscopy (e.g. antibiotic prophylaxis), and request of on demand sedation.

Primary outcome measure (for male and female subjects).

	_
Real time maximum insertion	_
pain (RTMIP) (unblinded) score	
(validation by correlation with	
recalled pain described below)	

Pain during insertion reported to the unblinded assisting nurse, visual analogue scale, VAS: 0=none, 10=most severe. The highest pain score will be tabulated for analysis. Timing of data collection will be at the discretion of the nurse to minimize bias by colonoscopist behavior.

Secondary outcome measures (for male and female subjects).

Proportion with no insertion pain Proportion report no pain during insertion of the colonoscope. Quality marker.

Insertion time	Time to cecum (clock display on monitor). Faster insertion is a quality marker
Proximal colon ADR	ADR from cecum to splenic flexure. Measure of high quality colonoscopy

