Bowel preparation. Standardized split dose minimizes differences in bowel preparation quality. Trained support staff will provide the instructions to minimize variations in patient compliance. Efforts will be made (e.g., telephone reminders by research coordinator) to encourage proper compliance. The most up-to-date purge preparation will be used. Standard instructions will be provided by the schedulers. There are variations in the bowel regimen at participating sites at present. The preparation will be standardized during the start-up period. Veterans with diabetes, chronic constipation, or known history of poor bowel preparation will be asked to refrain from solid food intake for an extra day before colonoscopy.

Patient blinding. An air filled surrounding results in unblinding of the cap (rim around the tip). Several measures will be used to blind the patients. 1. The patients will not be informed of the technique (with or without cap), and what the cap at the tip looks like. 2. The colonoscope will be set up in the absence of the patient. 2. Before the start, a small towel will cover the eyes of the patients, and care will be taken not to

uncover the eyes when the patient is moved. Upon confirmation of arrival to the water-filled cecum (passing ileocecal valve, viewing the appendix opening and touching the cecal floor, or intubation of the terminal ileum), the patient will be asked to guess which technique has been used. If the correct guesses are <60%, adequate blinding during insertion will be assumed (3,4). As an accepted benefit of unsedated colonoscopy, the patient can observe and ask questions during the withdrawal phase. Air will be used to distend the lumen for inspection, and biopsy or polypectomy during withdrawal in all patients.

Adjunct maneuvers. These will include loop reduction, patient position change and abdominal compression. They will be employed in the order as listed to minimize assistant hand/wrist injury. Loop reduction will be applied whenever insertion is not associated with advancement of the tip of the colonoscope in the lumen. Position change will be employed whenever the tip of the colonoscope fails to advance despite loop reduction. Abdominal compression will be employed when both of the above fail to permit advancement of the colonoscope. The number of times application of these maneuvers is employed will be recorded for analysis.

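### Whether the patient guessed the arm correctly should not be a candidate predictor of RTMIP: its interaction with group is the guess itself, and the guess follows the pain

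*SAP*

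**What the plan says.** Protocol section (4)(b), Patient blinding, fixes the timing: "Upon confirmation of arrival to the water-filled cecum", "the patient will be asked to guess which technique has been used". The primary outcome measure in the same section is the worst pain during insertion: "The highest pain score will be tabulated for analysis". RTMIP is therefore complete before the guess is made.

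Protocol Table 10 lists adequacy of patient blinding among the procedure and patient-level covariates, defined as "Patient guesses which method is used (<60% correct=adequate"). That 60% limit describes a group, not a patient.

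The SAP, under Primary hypothesis, plans mixed effects regressions to "evaluate the effects of potential covariates/confounds described in Tables 9 and 10". Each covariate enters with group and gender, "as well as the covariate by group interaction". A multiple model then takes the covariates "found to be significant (either as a main effect or an interaction effect"), along with group. The table under Exploratory hypotheses, where co-variables are said to affect the RTMIP report, names the variable again as a binary item: "Adequacy of patient blinding (yes, no); Loop reduction maneuvers (yes, no").

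Neither document defines the coding per patient, excludes the variable because it follows the outcome, or warns that pain may drive the guess.

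**The concern.** A predictor that is said to affect an outcome should not be determined after it. Patients have had both methods explained (abbreviated Protocol, section III, item 6) and know that the study concerns insertion pain. At the cecum they may well use the pain they have just felt to choose an answer. The regression would pick this up as an association between blinding and RTMIP even if no patient had any real clue to the arm.

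RTMIP is reported to an unblinded nurse, so readers will look closely at the evidence on blinding. The report could state that blinding was adequate under the 60% rule and also list blinding as a significant predictor or effect modifier of the primary outcome. The second statement would be uninterpretable, and it could be used to discredit or to explain away the RTMIP result.

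Patients in whom the cecum is not reached, including those stopped for pain, have no scheduled guess. They would drop out of this model, although the SAP says that all randomized patients are analysed.

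**Working it through.** **Step 1: the identity.** Code arm t = +1 (WECAC) or −1 (WE), guess g = +1 (cap) or −1 (no cap), and correct c = +1 or −1. Then c = g·t, so c·t = g·t² = g. The correct-by-group interaction is the main effect of the guess. On a random data set the two t statistics agree exactly (0.21436 in both).

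In 0/1 coding, let δ0 and δ1 be the mean RTMIP difference, guess cap minus guess no cap, in WE and WECAC. The coefficient of correct is −δ0 and the interaction is δ0 + δ1. Both are associations of pain with guess.

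**Step 2: inputs for the size.** The SAP sample size section gives RTMIP means (SD) of 2.7 (2.2) for WE and 1.5 (2.1) for WECAC in men, and 6.2 (3.5) and 3.5 (3.7) in women. Its evaluable totals are 144 and 86. A t-test calculation at alpha 0.0492 and 90% power, with 1.2/2.2 = 0.545 SD, reproduces the stated 72 men per group. For women, 0.7 SD gives 45 against 43 stated, which is immaterial here. The simulated trial has 144 + 86 = 230 patients, 1:1 within sex, with SD 2.2 in men and 3.6 in women, and scores limited to 0–10.

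Blinding is perfect: the guess depends on the patient's own pain and never on arm, with logit P(guess cap) = −b(RTMIP − 4). The documents give no value for b, so a range is assumed. The model is least squares of RTMIP on group, gender, correct and group × correct, without the site and provider random effects.

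**Step 3: false signals with no treatment effect (approximate).**

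| b per VAS point | Fall in odds of guessing cap | Guess cap: RTMIP <4 / ≥4 | Either term p<0.05 | Either term p<0.05/30 |
|---|---|---|---|---|
| 0 | 0% | 50% / 50% | 8% | 0.5% |
| 0.05 | 5% | 53% / 47% | 20% | 2% |
| 0.1 | 10% | 55% / 43% | 48% | 9% |
| 0.2 | 18% | 60% / 38% | 95% | 67% |
| 0.3 | 26% | 65% / 33% | 100% | 98% |

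The 8% at b = 0 comes from testing two terms; the interaction alone rejects in 4.8%. Correct guesses average 50%, and the 60% rule is met in over 99% of runs. If the link is reversed, so that more pain leads to guessing the cap, rejection at 0.2 is again 95%.

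**Step 4: the group coefficient with the planned effect.** The group + gender model gives about −1.47. With the interaction kept:

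| b | Wrong guessers | Correct guessers | Share correct | Average weighted by share |
|---|---|---|---|---|
| 0.1 | −0.89 | −1.99 | 0.519 | 0.481(−0.89) + 0.519(−1.99) = −1.46 |
| 0.2 | −0.29 | −2.48 | 0.534 | 0.466(−0.29) + 0.534(−2.48) = −1.46 |
| 0.3 | +0.25 | −2.89 | 0.548 | 0.452(+0.25) + 0.548(−2.89) = −1.47 |

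With correct entered without its interaction, the group coefficient is −1.46, −1.46 and −1.48. Using 142 men and 88 women with a female SD of 3.5 moves −0.29 to −0.34 and +0.25 to +0.20.

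**The case against.** - **Harm to the treatment estimate.** A reader might infer from the wrong-guesser column that this analysis removes or reverses the benefit of the cap. The documents do not support that. The 0/1-coded group coefficient is one of two conditional contrasts; the other is larger than the overall effect, and their weighted average is undistorted. The SAP does not say that interactions are kept in the final model, nor that this coefficient will be read as the treatment effect. This objection stands.
- **Threshold.** The SAP plans Benjamini-Hochberg control for the exploratory analyses, so raw 0.05 overstates the rates. This stands in part. The number of tests is not given; 30 is assumed, and the real rate lies between the two columns of Step 3. The control does not cure the interpretation, because the association is real but can run from pain to guess.
- **Link.** Patients are not told their technique or what the cap looks like, and nothing says that they are told the cap should hurt less. The strength of the link is indeed unknown, and with no link the interaction test keeps its 5% level. Some guesses could also reflect true unblinding; the model cannot separate the two.
- **Coding.** Correct or not is an inference, and the SAP's prose list of factors omits blinding. However, at group level the variable is constant and cannot be a regressor, and if the raw guess were entered its main effect would carry the same problem.
- **Narrowness.** Satisfaction and willingness to repeat are also Table 10 items recorded after insertion. That is true, but it does not answer this point.

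**Conclusion.** The point holds, at minor severity. Under the SAP's screening rule, the blinding term or its interaction with group can be significant when blinding is perfect, and it cannot be read as an effect of blinding on pain. The identity and the order of events need only the reading of the variable as guess correct, yes or no. The size rests on the assumed pain-guess link: from the nominal level with no link to near certainty at 0.3 per point, and from about 9% to 48% at 0.1 depending on how strict the false-discovery control proves to be.

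The distortion belongs to the interaction model. With no treatment effect, correct entered alone rejects in 2.6% to 5.6% of runs. The primary t-test or Mann-Whitney test does not use the guess and is unaffected. Nothing here shows that blinding will fail.

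**What to change.** In the SAP table under Exploratory hypotheses, delete adequacy of patient blinding from the RTMIP predictors. Under Primary hypothesis, exclude it from the Table 10 candidates. Report instead a table of guess by arm, with RTMIP summarised by guess within arm, as description only. State that an association between guess and RTMIP may arise from guessing informed by pain and will not be read as an effect of unblinding on pain. The 60% rule can stay as the group-level description.

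The cost is SAP wording and the loss of one exploratory regression line that could not have been interpreted. No data collection changes.
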